## 8 Safety and Adverse Events

### 8.1 Definitions

#### Unanticipated Problems Involving Risk to Subjects or Others

Any incident, experience, or outcome that meets all of the following criteria:

- Unexpected in nature, severity, or frequency (i.e. not described in study-related documents such as the IRB-approved protocol or consent form, the investigators brochure, etc.)
- Related or possibly related to participation in the research (i.e. possibly related means there is a reasonable possibility that the incident experience, or outcome may have been caused by the procedures involved in the research)
- Suggests that the research places subjects or others at greater risk of harm (including physical, psychological, economic, or social harm).

#### ADVERSE EVENT (AE)

An **adverse event (AE)** is defined as any symptom, sign, illness or experience that develops or worsens in severity during the course of the study. Intercurrent illnesses or injuries should be regarded as adverse events. An AE also includes any worsening (i.e., any clinically significant change in frequency and/or intensity) of a pre-existing condition that is temporally associated with the use of the study drug.

Abnormal results of diagnostic procedures are considered to be adverse events if the abnormality:

- results in study withdrawal
- is associated with a serious adverse event
- is associated with clinical signs or symptoms
- leads to additional treatment or to further diagnostic tests
- is considered by the investigator to be of clinical significance

Adverse events can be spontaneously reported or elicited during open-ended questioning, examination, or evaluation of a subject. (In order to prevent reporting bias, subjects should not be questioned regarding the specific occurrence of one or more AEs.)

#### SERIOUS ADVERSE EVENT (SAE)

Adverse events are classified as serious or non-serious. A **serious adverse event** is any AE that is:

- fatal
- life-threatening (defined as an event in which the participant was at risk of death at the time of the event; it does not refer to an event which hypothetically might have caused death if it were more severe)
- requires or prolongs in-patient hospital stay (In-patient hospitalization is defined as admission to a hospital or an emergency room for longer than 24 hours. Prolongation of existing hospitalization is defined as a hospital stay that is longer than was originally anticipated for the event, or is prolonged due to the development of a new AE as determined by the investigator or treating physician. Hospitalization or prolongation of existing hospitalization due to the progression of

CONFIDENTIAL

This material is the property of the NYU School of Medicine. Do not disclose or use except as authorized in writing by the study sponsor

underlying malignancy will not be considered an SAE, if it is clearly consistent with the typical progression pattern of the underlying cancer (see **NOTE** below).

- results in persistent or significant disability or incapacity (substantial disruption of one's ability to conduct normal life functions)
- a congenital anomaly or birth defect
- an important medical event - Important medical events are those that may not be immediately life threatening, but are clearly of major clinical significance. They may jeopardize the subject, and may require intervention to prevent one of the other serious outcomes noted above. For example, drug overdose or abuse, a seizure that did not result in in-patient hospitalization, or intensive treatment of bronchospasm in an emergency department would typically be considered serious. Potential drug induced liver injury (DILI) is also considered an important medical event (see below for the definition of potential DILI).
- Suspected transmission of an infectious agent (eg, pathogenic or nonpathogenic) via the study drug.
- Any component of a study endpoint that is considered related to study therapy should be reported as an SAE (eg, death is an endpoint, if death occurred due to anaphylaxis, anaphylaxis must be reported).

Although pregnancy, study drug overdose, potential drug-induced liver injury (DILI), and development of another cancer are not always serious by regulatory definition, these events must be handled as SAEs.

#### **NOTE: Hospitalization, Prolonged Hospitalization or Surgery**

Any adverse event that results in hospitalization or prolonged hospitalization should be documented and reported as a serious adverse event unless specifically instructed otherwise in this protocol. Any condition responsible for surgery should be documented as an adverse event if the condition meets the criteria for an adverse event.

Exceptions: Neither the condition, hospitalization, prolonged hospitalization, nor surgery are reported as an adverse event in the following circumstances:

- A visit to the emergency room or other hospital department < 24 hours, that does not result in admission (unless considered an important medical or life-threatening event)
- Hospitalization or prolonged hospitalization for diagnostic or elective surgical procedures for a preexisting condition. Surgery should **not** be reported as an outcome of an adverse event if the purpose of the surgery was elective or diagnostic and the outcome was uneventful.
- Hospitalization or prolonged hospitalization required to allow efficacy measurement for the study.
- Hospitalization as per protocol for a planned medical/surgical procedure
- Routine health assessment requiring admission for baseline/trending of health status (e.g., routine colonoscopy)
- Medical/surgical admission other than to remedy ill health and planned prior to entry into the study. Appropriate documentation is required in these cases.
- Hospitalization or prolonged hospitalization for therapy of the target disease of the study, unless it is a worsening or increase in frequency of hospital admissions as judged by the clinical investigator.
- Admission encountered for another life circumstance that carries no bearing on health status and requires no medical/surgical intervention (eg, lack of housing, economic inadequacy, caregiver respite, family circumstances, administrative reason).
- Admission for administration of anticancer therapy in the absence of any other SAEs.

#### **NON-SERIOUS ADVERSE EVENT**

All adverse events that do not meet any of the criteria for **Serious Adverse Event** (defined above) should be regarded as **non-serious adverse events**.

#### **Progression of underlying malignancy**

CONFIDENTIAL

This material is the property of the NYU School of Medicine. Do not disclose or use except as authorized in writing by the study sponsor

Progression of underlying malignancy will not be considered an AE if it is clearly consistent with the typical progression pattern of the underlying cancer (including time course, affected organs, etc.). Hospitalization or death due solely to manifestations consistent with typical progression of underlying malignancy will not be considered a SAE. Clinical symptoms of progression may be reported as AEs if the symptom cannot be determined as exclusively due to the progression of the underlying malignancy, or does not fit the expected pattern of progression for the disease under study.

If there is any uncertainty about an AE being due only to progression of the underlying malignancy, it should be reported as an AE or SAE as outlined in Section 8.4.

#### **Adverse Event Reporting Period**

All Adverse Events (AEs) and Serious Adverse Events (SAEs) that occur following the subject's written consent to participate in the study and for a minimum of 100 days after the last dose of nivolumab and 90 days after the last dose of ipilimumab must be reported per the guidelines in Section 8.4, whether related or not related to study drug. If applicable, SAEs must be collected that relate to any later protocol-specified procedure (e.g., an optional tumor biopsy).

Non-serious AEs should be followed to resolution or stabilization, or reported as SAEs if they become serious. Follow-up is also required for non-serious AEs that cause interruption or discontinuation of study drug and for those present at the end of study treatment as appropriate.

#### **Preexisting Condition**

A preexisting condition is one that is present at the start of the study. A preexisting condition should be recorded as an adverse event if the frequency, intensity, or the character of the condition worsens during the study period.

#### **General Physical Examination Findings**

At screening, any clinically significant abnormality should be recorded as a preexisting condition. At the end of the study, any new clinically significant findings/abnormalities that meet the definition of an adverse event must also be recorded and documented as an adverse event.

#### **Post-study Adverse Event**

All unresolved adverse events should be followed by the investigator until the events are resolved, the subject is lost to follow-up, or the adverse event is otherwise explained. At the last scheduled visit, the investigator should instruct each subject to report any subsequent event(s) that the subject, or the subject's personal physician, believes might reasonably be related to participation in this study. The investigator should notify the study sponsor of any death or adverse event occurring at any time after a subject has discontinued or terminated study participation that may reasonably be related to this study. The sponsor should also be notified if the investigator should become aware of the development of cancer or of a congenital anomaly in a subsequently conceived offspring of a subject that has participated in this study.

#### **Abnormal Laboratory Values**

All laboratory test results captured as part of the study should be recorded following institutional procedures.

A clinical laboratory abnormality should be documented as an adverse event if any one of the following conditions is met:

- The laboratory abnormality is not otherwise refuted by a repeat test to confirm the abnormality
- The abnormality suggests a disease and/or organ toxicity
- The abnormality is of a degree that requires active management; e.g. more frequent follow-up assessments, further diagnostic investigation, specific corrective therapy, etc.
- The abnormality leads to a change in dosing (outside of protocol-stipulated dose adjustments)
- The abnormality leads to discontinuation from the study, significant additional concomitant medication, or other therapy
- The laboratory test result is clinically significant or meets the definition of an SAE

CONFIDENTIAL

This material is the property of the NYU School of Medicine. Do not disclose or use except as authorized in writing by the study sponsor

Contact the sponsor in the event the investigator feels that an abnormal test finding should be reported as an AE, although it does not meet any of the above criteria.

Test results that constitute SAEs should be documented and reported as such per the guidelines outlined in Section 8.4.

Repeating an abnormal test, in the absence of any of the above conditions, does not constitute an AE. Any abnormal test result that is determined to be an error does not require reporting as an AE.

Evaluation of severity of laboratory abnormalities will be assessed according to the scale outlined in Section 8.2.1.

### **Potential Drug Induced Liver Injury (DILI)**

Wherever possible, timely confirmation of initial liver-related laboratory abnormalities should occur prior to the reporting of a potential DILI event. All occurrences of potential DILIs, meeting the defined criteria, must be reported as SAEs (see Section 8.4 for reporting details).

Potential drug induced liver injury (DILI) is defined as:

- 1) AT (ALT or AST) elevation > 3 times upper limit of normal (ULN)

AND

- 1) Total bilirubin > 2 times ULN, without initial findings of cholestasis (elevated serum alkaline phosphatase)

AND

- 3) No other immediately apparent possible causes of AT elevation and hyperbilirubinemia, including, but not limited to, viral hepatitis, pre-existing chronic or acute liver disease, or the administration of other drug(s) known to be hepatotoxic.

### **Pregnancy**

If, following initiation of the investigational product, it is subsequently discovered that a study participant is pregnant or may have been pregnant at the time of investigational product exposure, including during at least 5 half-lives after product administration (within 5 months after the last dose of study drug for a female subject and within of 7 months after the last dose of study drug for a male subject), the investigational product will be permanently discontinued in an appropriate manner (eg, dose tapering if necessary for participant).

The investigator must immediately notify [[contact]](mailto:[contact]) of this event via the **Pregnancy Surveillance Form** [provided upon request from BMS] in accordance with SAE reporting procedures. The investigator must also immediately notify the Sponsor/Overall PI of the event.

Protocol-required procedures for study discontinuation and follow-up must be performed on the participant. Follow-up information regarding the course of the pregnancy, including perinatal and neonatal outcome and, where applicable, offspring information must be reported on the Pregnancy Surveillance Form.

Any pregnancy that occurs in a female partner of a male study participant should be reported to BMS. Information on this pregnancy will be collected on the Pregnancy Surveillance Form. In order for Sponsor or designee to collect any pregnancy surveillance information from the female partner, the female partner must sign an informed consent form for disclosure of this information.

### **Overdose**

CONFIDENTIAL

This material is the property of the NYU School of Medicine. Do not disclose or use except as authorized in writing by the study sponsor

An overdose is defined as the accidental or intentional administration of any dose of a product that is considered both excessive and medically important. All occurrences of overdose must be reported as an SAE.

### **Other Safety Considerations**

Any significant worsening noted during interim or final physical examinations, electrocardiograms, X-rays, and any other potential safety assessments, whether or not these procedures are required by the protocol, should also be recorded as a non-serious or serious AE, as appropriate, and reported accordingly.

### **Expected Adverse Events for Nivolumab and Ipilimumab**

For the purpose of regulatory reporting requirements during clinical development, the following AEs will be considered as **expected** and meet the threshold of causal association (based on comprehensive medical evaluation considering the mechanism of action and temporal relationship after excluding other possible etiologies) defined by nivolumab and ipilimumab based on safety data from completed and ongoing clinical studies:

- Infusion-related reactions including drug hypersensitivity reactions
- Immune-mediated adverse reactions such as immune-mediated colitis, immune-mediated hepatitis including autoimmune hepatitis, immune-mediated thyroid disorders including hyperthyroidism, hypothyroidism, thyroiditis and autoimmune thyroiditis, immune-mediated pneumonitis, immune-mediated skin reactions including rash, pruritus, rash generalized, rash maculo-papular, erythema, pemphigoid, other immune-mediated reactions including myocarditis, adrenal insufficiency, uveitis, iritis, myositis.

### **Expected Adverse Events for Radiation Therapy**

Development of edema in the brain is common following brain radiation therapy and may be asymptomatic (solely a radiographic finding) or associated with mild, moderate or severe symptoms. Therefore, brain edema will be considered an expected event related to study therapy (RT). Additionally, alopecia, fatigue, transient worsening of baseline neurological symptoms, seizures, skin irritation, neurocognitive dysfunction and cerebral radiation necrosis are all expected adverse events associated with radiation therapy.

## **8.2 Evaluation of Severity and Causality**

### **8.2.1 Evaluation of Severity**

The severity of AEs (including test findings classified as AEs) will be graded using the current version of the National Cancer Institute-Common Terminology Criteria for Adverse Events (NCI-CTCAE) grading system. Adverse events not listed in the NCI-CTCAE, will be graded according to the following scale:

1 (Mild):	Mild; asymptomatic or mild symptoms; clinical or diagnostic observations only; intervention not indicated.
2 (Moderate):	Moderate; minimal, local or noninvasive intervention indicated; limiting age-appropriate instrumental ADL*.
3 (Severe):	Severe or medically significant but not immediately life-threatening; hospitalization or prolongation of hospitalization indicated; disabling; limiting self-care ADL**.
4 (Life-threatening):	Life-threatening consequences; urgent intervention indicated.
5 (Death):	Death related to AE.

CONFIDENTIAL

This material is the property of the NYU School of Medicine. Do not disclose or use except as authorized in writing by the study sponsor

\* Instrumental Activities of Daily Living (ADL) refer to preparing meals, shopping for groceries or clothes, using the telephone, managing money, etc.

\*\*Self-care ADL refer to bathing, dressing and undressing, feeding self, using the toilet, taking medications, and not bedridden.

## 8.2.2 Evaluation of Causality

### **Relationship of AEs to Study Drug:**

The relationship of AEs to study drug will be assessed by the investigator, and will be a clinical decision based on all available information. The following question will be addressed:

Is there a reasonable possibility that the AE may have been caused by the study drug?

The possible answers are:

**Not Related:** There is no reasonable possibility that the event may have been caused by the study drug

**Related:** There is a reasonable possibility that the event may have been caused by the study drug.

The sponsor will request information to justify the causality assessment of SAEs, as needed.

If the investigator believes that an SAE is not related to study drug, but is potentially related to the conditions of the study (such as withdrawal of previous therapy or a complication of a study procedure), the relationship should be specified in the narrative section of the SAE Report Form.

**Appendix 5** lists factors to consider in assessing the relationship of AEs to nivolumab, ipilimumab, infusion procedures, radiation therapy, combination treatment, or study procedures.

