### **3.5 Primary Safety Endpoints**

#### **3.5.1 Phase II Safety Analysis**

For the phase II portion of the study, we consider a rate of unacceptable toxicity of 40% or greater (defined as CTCAE grade 3, grade 4, or intolerable grade 2 toxicity that is possibly, probably, or definitely related to study therapy) to be unacceptable. Intolerable grade 2 toxicity will be defined as any grade 2 toxicity that results in study discontinuation. Monitoring for toxicity will follow a Bayesian-based rule for the probability that the rate of unacceptable toxicity exceeds a maximal tolerated level of 40%. We will assume a *Beta*(2,3) prior, which is prior information equivalent to two unacceptable toxicities observed in 5 treated patients. This minimally informative prior is justified as there is some clinical experience with the combination therapy. Early termination for unacceptable toxicity will be considered based on a posterior probability (in parentheses), that the unacceptable toxicity rate exceeds 30%. Toxicity will be carefully monitored in the 24 Phase II patients. Termination will be considered if unacceptable toxicity is observed in: 2 of 3 patients (0.71), 4 of 6 patients (0.83), 5 of 9 patients (0.77), 7 of 12 patients (0.86), 8 of 15 patients (0.81), 9 of 18 patients (0.77), 11 of 21 patients (0.85), or 12 of 24 patients (0.81).

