#### **3.5.2 Special Interim Safety Analysis**

A special interim analysis for evaluation of late delayed radiation therapy adverse events (occurring 3 months or more after radiation therapy treatment) will be conducted due to a possible increased incidence of CNS toxicity from delayed radiation necrosis or radiation injury occurring during the first 6 months post RT. After the first 12 subjects treated, including subjects in the Safety Lead-In portion of the trial, have a minimum 24 week overall survival follow-up time, an interim safety analysis for delayed treatment-induced neurotoxicity will be performed. If the incidence of CTCAE grade  $\geq 3$  CNS (neurologic) toxicity deemed possibly, probably, or definitely related to treatment is 33% or higher (i.e., 4 or more subjects of the first 12) in this group, the trial will be halted due to lack of safety.

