## **8.4 Reporting of Serious Adverse Events and Unanticipated Problems**

The investigator (or designee) will seek information on AEs at each patient contact, and record all AEs that occur from the time the informed consent is signed until 30 days after the end of study treatment. CTCAE version 4.03 terms should be used.

All AEs after initiation of study treatment and until 30 days after the last study treatment, regardless of relationship to study treatment, will be reported. Additionally, any SAE or other AE of concern that the investigator believes may be related to study treatment and that occurs later than 30 days after last study treatment should be reported. Information for any nonserious AE that starts during the treatment period or within 30 days after last treatment will be collected from the time of the event until resolution of the event, or until the patient's last study visit, whichever comes first. Serious adverse event information will be collected until the event is considered chronic and/or stable.

Study treatment includes nivolumab, ipilimumab and radiation therapy.

Investigators and the protocol sponsor must conform to the adverse event reporting timelines, formats and requirements of the various entities to which they are responsible, but at a minimum those events that must be reported are those that are:

- related to study participation,
- unexpected, and
- serious or involve risks to subjects or others (see definitions, section 8.1).

Note: Immediately reportable criteria must be reported to the IRB at each annual review.

Serious adverse event reporting will begin in conjunction with the date of informed consent. Any SAEs occurring prior to study drug administration that the investigator believes may have been caused by a protocol procedure must be reported immediately to the Sponsor or its designee and recorded on the case report form.

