All fatal or life-threatening adverse events must be immediately reported to the Sponsor by telephone or e-mail. Within 24 hours of the event, the Serious Adverse Event (SAE) Form supplied by NYUSoM must be faxed to the Sponsor (Overall PI), who must then inform the NYUSoM IRB, PCC CTO, and DSMC within 24 hours of the event whether full information regarding the event is known or not. Additional follow-up by the investigator will be required if complete information is not known. De-identified source documentation of all examinations, diagnostic procedures, etc. which were completed with respect to the event should be included with the SAE form. Care should be taken to ensure that the patient's identity is protected and the patient's identifiers (as assigned at the time of study enrollment) are properly mentioned on any copy of source document provided to the Sponsor. For laboratory results, include the laboratory normal ranges.

In case of accidental or intentional overdose of study drug (nivolumab and/or ipilimumab), even if asymptomatic or not fulfilling a seriousness criterion, the overdose is to be reported to the Sponsor immediately (within 1 working day) using the AE and SAE forms supplied by NYUSoM. Overdose of study drug is defined in Section 8.1.

All serious adverse events (SAEs) will be evaluated by the DSMC. If meeting the requirements for expedited reporting, the Sponsor will report the adverse event to all regulatory authorities with jurisdiction over ongoing trials with the study drug and to all other investigators involved in clinical trials with the study drug. The investigator is responsible for reporting all SAEs to the appropriate IRB, DSMC, and FDA.

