**No:**

- due to external causes such as environmental factors or other treatment/s being administered
- due to the patient's/subject's disease state or clinical condition
- do not follow a reasonable temporal sequence following the time of administration of the dose of nivolumab or ipilimumab, study procedure, or combination treatment
- do not reappear or worsen when dosing with nivolumab or ipilimumab, study procedure, or combination treatment is resumed
- are not a known response to nivolumab or ipilimumab or infusion procedure, study procedure, or combination treatment based upon pre-clinical data or prior clinical data

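### Causality is defined only against study drug, so toxicity attributed solely to radiotherapy can be missed by the two phase II safety rules

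*Combined protocol and SAP*

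**What the plan says.** **What is recorded.** Section 8.2.2 is the only section that defines how causality is assessed. The investigator answers "Is there a reasonable possibility that the AE may have been caused by the study drug" with Related or Not Related. Not Related means "There is no reasonable possibility that the event may have been caused by the study drug". For a serious event judged unrelated to drug but linked to study conditions, the relationship goes in the SAE narrative.

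**What the terms cover.** The overdose paragraph of Section 8.4 spells out study drug: "In case of accidental or intentional overdose of study drug (nivolumab and/or ipilimumab". Section 7.2.1 lists study drug and radiation as separate items. Section 8.4 says "Study treatment includes nivolumab, ipilimumab and radiation therapy". Section 8.1 classes brain edema as an expected event of study therapy and puts RT in brackets after that term.

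**What the rules count.** The Bayesian rule in 3.5.1 counts "toxicity that is possibly, probably, or definitely related to study therapy", and termination is considered when a boundary is reached. The CNS rule in 3.5.2 halts the trial if the incidence of grade 3 or higher CNS "toxicity deemed possibly, probably, or definitely related to treatment is 33% or higher", that is, 4 or more of the first 12 subjects. Its stated purpose is late delayed radiation effects.

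**What the guidance says.** Section 8.2.2 points to Appendix 5 for factors that it says cover radiation therapy. In the body, Appendix 5 is the management algorithms. The causality factors are in Section 15.6, headed Appendix 6 there, although the table of contents still lists them as Appendix 5. That list never names radiation, and a reason to answer No is "due to external causes such as environmental factors or other treatment/s being administered".

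**The concern.** A safety rule should be computable from the data that the protocol says to collect. Here the recorded attribution covers two of the three treatment components, and the rules need all three. The component left out is the one that the CNS interim was set up to watch. Any loss acts in one direction, toward not reaching a boundary, and 3.5.2 is a mandatory halt rather than a prompt for discussion.

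**Working it through.** **1. Trace one event through the text.** Take a non-serious grade 3 CNS event that the investigator attributes to RT only. Section 6.2.7 foresees this attribution when it separates events due solely to RT from those due to the drugs.

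- Under 8.2.2 the question concerns study drug, so the answer is Not Related.
- The SAE narrative does not apply, because the event is not serious.
- Under 3.5.1 and 3.5.2 the event should count, because study therapy and treatment include RT.
- No passage converts the 8.2.2 answer into the attribution used in 3.5, or says which record feeds those rules.

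**2. Reproduce the plan's figures.** The CNS boundary is 4/12 = 0.333, which agrees with the stated 33%. For the Bayesian rule, P(rate > 0.40 | Beta(2+r, 3+n−r)) gives 0.710, 0.834, 0.771, 0.858, 0.814, 0.772, 0.846 and 0.813 for 2/3, 4/6, 5/9, 7/12, 8/15, 9/18, 11/21 and 12/24. All eight match the printed values after rounding.

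**3. Illustrate the CNS rule.** Let p be the true share of subjects with a treatment-related grade 3 or higher CNS event. Let f be the share of those events recorded as Not Related. The documents give neither, so both are assumptions. With independent losses, the counted rate is q = p(1−f) and

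P(halt) = 1 − Σ C(12,x) q^x (1−q)^(12−x), summed over x = 0 to 3.

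At p = 1/3:

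- f = 0, q = 1/3: 1 − (0.0077 + 0.0462 + 0.1272 + 0.2120) = 0.607
- f = 0.25, q = 0.25: 1 − (0.0317 + 0.1267 + 0.2323 + 0.2581) = 0.351
- f = 0.50, q = 1/6: 1 − (0.1122 + 0.2692 + 0.2961 + 0.1974) = 0.125

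| True rate p | f = 0 | f = 0.25 | f = 0.50 |
|---|---|---|---|
| 0.20 | 0.205 | 0.092 | 0.026 |
| 1/3 | 0.607 | 0.351 | 0.125 |
| 0.40 | 0.775 | 0.507 | 0.205 |
| 0.50 | 0.927 | 0.718 | 0.351 |

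**4. Illustrate the Bayesian rule.** This is the exact probability of reaching any of the eight printed boundaries by 24 subjects, with the counted rate again p(1−f).

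| True rate p | f = 0 | f = 0.25 | f = 0.50 |
|---|---|---|---|
| 0.40 | 0.532 | 0.278 | 0.115 |
| 0.50 | 0.798 | 0.463 | 0.185 |
| 0.60 | 0.953 | 0.673 | 0.278 |

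Here f is a share of all unacceptable toxicity. Drug-related immune events would be recorded correctly, so the lost share should be smaller than for the CNS rule.

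**The case against.** The strongest reply is that nobody running the CNS interim would discard radiation necrosis. Section 3.5.2 states its own standard and purpose. Sections 6.2.5 and 8.1 tie brain edema to RT, and the protocol says that such events may be reviewed in phase II toxicity monitoring. All adverse events are collected whatever their relationship, and the DSMC reviews them quarterly. The AE form is not in the documents and may already have an RT field. The question heading the causality appendix mentions concomitant treatment, and its Yes list mentions combination treatment, so RT can be read in. Finally, Not Related requires no reasonable possibility of a drug cause. Section 1.3.3 calls radiation necrosis partly immune-mediated and says that immunotherapy might potentiate it, so an investigator who accepts this would seldom exclude the drugs.

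Most of this stands as a limit on size. Under-counting is possible, not certain, and Section 1.3.3 makes a large lost share less likely. It does not close the gap: none of these passages supplies a defined RT attribution for every event or links one to the rules in 3.5.

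A reader might infer three stronger things, which the documents do not support:

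- *RT-caused events also drop out of the DLT count.* Sections 6.1.1 and 6.1.1.1 name RT in the DLT definition and give the final decision to the sponsor and the DSMC.
- *A two-level record cannot feed a three-level rule.* Possibly, probably and definitely all count alike, so a reasonable-possibility answer carries the same information once it covers RT.
- *Events will be graded under two CTCAE versions.* Section 8.2.1 does say severity "will be graded using the current version of the National Cancer Institute-Common Terminology Criteria for Adverse Events", but the abbreviations list and many sections fix version 4.03. The documents do not show that another version would change any grade.

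**Conclusion.** The point holds for the two phase II rules. As written, an event attributed solely to RT is Not Related under 8.2.2 and can be missed by the Bayesian rule and the CNS halt. This should be corrected, because 3.5.2 is a binding halt aimed at late radiation toxicity. The conclusion rests on the protocol's use of study drug for the two antibodies, and on reading study therapy and treatment in 3.5 as including RT. Sections 8.1 and 8.4 and the purpose of 3.5.2 support that reading, although 3.5 does not spell it out.

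The size is unknown. The fall from 0.61 to 0.35 or 0.13 shows only how sensitive a 4-of-12 rule is to assumed losses of a quarter or a half. It does not forecast what will happen in this trial.

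**What to change.** - In 8.2.2 and on the AE form, record relatedness separately for nivolumab, ipilimumab and RT. A reasonable-possibility yes/no for each is enough.
- In 3.5.1 and 3.5.2, state that an event counts if it is at least possibly related to any of the three.
- In the causality appendix, name protocol RT so that it is not read as another treatment, and correct the appendix number cited in 8.2.2.
- As minor tidying, replace the reference in 8.2.1 to the current CTCAE version with version 4.03.

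The cost is three short fields in place of one and a few wording changes. No visit, assessment, boundary or treatment rule changes. Because all adverse events are collected regardless of relationship, events already on file can be re-attributed.
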